In PsA but also in chronic arthritis in general, integrating imaging in clinical practice is the challenge of the near future and for clinical feasibility it is essential to identify an US composite score that could explore all the domains of the disease, especially in the polymorphic PsA.

In 2012 *Gutierrez et al.* developed a Power Doppler composite score focused on joints, tendons, entheses, skin and nails and the final target was to define the overall disease activity.⁽¹³⁾ The German US7-joints score is another viable tool for examining patients with chronic arthritis in daily practice. Developed mainly for RA, it was also effective for monitoring therapy in peripheral PsA.⁽¹⁴⁾ More recently *Ficjan et al* developed two new US composite scores (PsASon-13 and PsASon-22), derived from a total ultrasound score (68 joints/14 entheses) in order to have a high sensitivity to detect PsA features and a good feasibility in clinical practice.⁽¹⁵⁾ However no simplified scores are fully validated in terms of content, construct and criterion so far. For this reason extensive US evaluations are needed to assess PsA in clinical practice and research.

AIM

The aim of this study is to identify clinical and US predictors of achieving MDA in PsA patients with active peripheral arthritis starting a new course of therapy.

Identifying prognostic factors of achieving remission or low disease activity will allow a better selection of patients with poorer outcome and a following improvement of the therapeutic strategies. Furthermore the possibility that US could be an added prognostic value makes this study a clear example of integration between the clinic and US. This study will respond to the need of tailoring treatment that would allow clinicians to practice a more effective and personalized medicine, optimizing the outcomes of patients with PsA as well as the treatments management.

STUDY OBJECTIVES

PRIMARY OBJECTIVE

In clinically diagnosed PsA with clinically active joint disease starting a new course of therapy, to evaluate the additional value of US-score (US-score PsA-SIR) over clinical examination in detecting patients achieving MDA at 6 months.

SECONDARY OBJECTIVES

In clinically diagnosed PsA with clinically active joint disease starting a new course of therapy:

- to evaluate the additional value of US over clinical examination in detecting patients:
 - achieving MDA at 12 months (including sustained)

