A total of 30 static images per US-lesion type (synovitis, enthesitis, tenosynovitis, erosion, bony apposition) with 50% of presence of lesions will be submitted to scoring through an on-line electronic platform. A reference atlas will be provided to the investigators before the exercise. A second exercise could be offered to investigators who did not achieve a minimum level of kappa after further training at one of the Centres of the PIs.

SCREENING VISIT

The aim of this visit is to identify a patient who might be suitable for inclusion in the study.

- Consent: Inform the patient about the nature and objectives of the study and obtain his/her written informed consent;
- Check inclusion/exclusion criteria;
- Check cumulatively CASPAR criteria since the onset of PsA;
- Assign patient number (PN) in sequential order, if the patient is suitable for the inclusion in the study.

BASELINE VISIT

The aim of this visit is to confirm that the patient is appropriate for inclusion in the study, determine disease activity state, undertake a complete high resolution ultrasound assessment and X-ray of hands and feet. If a X-ray has been already done within the 6 months before the study entry is not requested to perform a further scanning.

- Record in Case Report Form:
 1. demographic and life-style variables (*smoking, alcohol consumption, BMI*);
 2. drug history (*including past adverse events*);
 3. typical comorbidities associated to PsA (*obesity, diabetes, hypertension, metabolic syndrome non-alcoholic fatty liver disease, IBD, uveitis, anxiety/depression*) and other comorbidities (*e.g. neoplasms, cardiovascular disease, Charlson comorbidity index*);
 4. onset of symptoms and disease duration;
 5. define clinical subset of PsA;
 6. CPR (mg/dl), ESR;
 7. RF, ACPA and HLA B27 (if available);
 8. treatment to be started;
- Procedures for psoriatic arthritis:
 1. Swollen (68) and Tender (66) Joints Count;
 2. Enthesal assessment;
 3. Tender Dactylitis Count;

- Procedures for psoriasis:
 1. Body Surface Area (BSA);
- Questionnaires:
 1. Physician completes VAS Physician global assessment of disease activity (joint and skin) 0-100;
 2. Patients completes pain VAS (0-100), global VAS (0-100), HAQ, BASDAI, PSAID12;
- US assessment:
 1. US-score PsA-SIR;
- X-ray assessment of hands and feet:
 1. Posterior-anterior radiographic assessments of hands and feet (electronic format)

3RD MONTH VISIT

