 1. Physician completes VAS Physician global assessment of disease activity (joint and skin) 0-100;
 2. Patients completes pain VAS (0-100), global VAS (0-100), HAQ, PsAID12
- US assessment:
 1. US-score PsA-SIR
- X-ray assessment of hands and feet:
 1. Posterior-anterior radiographic assessments of hands and feet (electronic format)

CLINICAL ASSESSMENT

The demographic variables describing the patients will be age, sex, ethnic group, family history, body weight, height and smoking. On enrolment in the study, a detailed medical history will be recorded mostly focusing on PsA (onset of symptoms, date of diagnosis), related treatment (current and previous medication, reason for withdrawal) and associated comorbidities (e.g. SpA spectrum comorbidities). To assess comorbidities, disease specific recommendations will be followed.⁽¹⁷⁾

To increase feasibility and reliability metabolic syndrome will be defined as follows: 1) BMI > 30 kg/m²; 2) a diagnosis of type 2 diabetes mellitus and 3) a diagnosis of hypertension.⁽¹⁸⁾

Each patient considered eligible for the study will be classified according to clinical subset(s) of PsA:

- 1- Monoarticular or asymmetric oligoarthritis with or without dactylitis.
- 2- Symmetric polyarthritis similar to rheumatoid arthritis.
- 3- Classic psoriatic arthritis confined to distal interphalangeal joints of hands and feet.
- 4- Spondylitis with or without peripheral joint involvement
- 5- Arthritis mutilans

CLINICAL EFFICACY

Clinical response and clinical remission will be based on the following variables:

- 1- Minimal Disease Activity (MDA)
- 2- Disease Activity for Psoriatic Arthritis (DAPSA)
- 3- ACR response score

The sonographer should be blinded to minimize bias associated with disease activity score evaluation. In addition, every effort should be made to ensure that the same member of staff performs the disease activity assessment on successive visits for a given patient.

The MDA calculation will be based on the evaluation of 7 variables:

- a) 68 tender joints count (≤ 1)
- b) 66 swollen joint count (≤ 1)
- c) BSA ≤ 3
- d) Patient pain VAS (≤ 15 mm);
- e) Patient global disease activity VAS (≤ 20 mm);
- f) HAQ (≤ 0.5);
- g) Leeds Enthesitis Index (LEI) tender enthesal points (≤ 1)

Patients will be classified as having MDA if they meet 5 out of these 7 criteria (value in brackets).

The DAPSA calculation is based on the evaluation of 5 variables:

- a) 68 tender joints count
- b) 66 swollen joint count

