LEI enthesal sites include the bilateral lateral epicondyles, medial femoral condyles, and Achilles tendon insertions. The 4 additional enthesal sites include: quadriceps insertion patella, inferior pole patella, tibial tubercle, insertion plantar fascia. Tenderness on examination is evaluated applying 4 kg/cm² of pressure (enough to blanch the tip of the examiner's fingernail) and recording tenderness as either present (1) or absent (0) for each of the 6 sites, for an overall score range of 0–6. Higher count represents greater enthesitis burden.

Dactylitis, or “sausage digit,” is characterized by swelling of an entire finger due to synovitis, tenosynovitis, enthesitis, and soft tissue edema. For the purpose of the UPSTREAM study, dactylitis will be assessed using:

- **Tender Dactylitis Count.**

Each of 20 fingers will be evaluated. The clinician marks which fingers are affected on a diagram displaying fingers and toes. The clinician squeezes the affected fingers with moderate pressure and documents the patient's response: 0 = no tenderness, 1 = tender.

Spinal assessment will be performed using:

- **Bath Ankylosing Spondylitis Disease Activity Index (BASDAI).**

The BASDAI consists of a 1 - 10 scale measuring discomfort, pain, and fatigue (1 being no problem and 10 being the worst problem) in response to six questions asked of the patient pertaining to the five major symptoms of AS: Fatigue - spinal pain – peripheral activity - morning stiffness duration - morning stiffness severity. To give each symptom equal weighting, the average of the two scores relating to morning stiffness is taken. The resulting 0 to 50 score is divided by 5 to give a final 0 – 10 BASDAI score.

Blood tests will be performed locally. ESR and CRP will be determined at each protocol time point and collected along with reference ranges.

SAFETY MONITORING

An adverse event (AE) is any untoward medical occurrence (i.e., any unfavourable and unintended sign (including abnormal laboratory findings), symptom or disease) in a subject after providing written informed consent for participation in the study. Therefore, an AE may or may not be temporally or causally associated with the use of a specific medicinal product.

DEFINITION OF SAE

An SAE is defined as any adverse event (appearance of (or worsening of any pre-existing) undesirable sign(s), symptom(s) or medical conditions(s) which meets any one of the following criteria:

- is fatal or life-threatening

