US IMAGING						
US-score PsA-SIR		X		X	X	X
CR IMAGING						
X ray (hands-feet)		X			X	X
ADVERSE EVENTS			X	X	X	X

STATISTICAL ANALYSIS PLAN

VARIABLES: OUTCOME MEASURES

PRIMARY:

- MDA at 6 months

SECONDARY

- MDA at 12 months, sustained MDA at 6 AND 12 months
- DAPSA <3.3 at 6 months, 12 months, 6 AND 12 months
- Δ mSvH 0-12 and 0-24 months
- Δ HAQ 0-12 and 0-24 months
- Δ PSAID 0-12 and 0-24 months
- US-score PsA-SIR damage subscore at 0-6-12 months

US PREDICTORS

- US-score PsA-SIR
- US-score PsA-SIR inflammation subscore
- US-score PsA-SIR damage subscore

CLINICAL PREDICTORS

Based on the relevant literature clinical variables to be considered in the model include:

- Demographic and environmental factors:
 - Age
 - Gender
 - Smoking
 - BMI
- Clinical factors:
 - subset of PsA
 - time from symptoms onset to diagnosis
 - disease duration
 - disease activity (DAPSA and BASDAI)
 - HAQ score
 - tender joints / pain
 - comorbidities (FM, MetS)
- Serological factors:
 - Acute phase reactants
- Therapy factors:
 - Treatment (NSAIDs, steroids, DMARDs)

DESCRIPTIVE ANALYSES

Descriptive data will be provided for all outcomes according to data type; number of patients (N), mean, standard deviation (for interval data), median 25% and 75% quartiles (for ordinal data). Frequency (absolute and relative) distributions will be provided for categorical data. Two-sided p-values will be presented throughout.

PRIMARY ENDPOINT ANALYSIS

Prediction of 6 months MDA will use multivariate adjusted logistic models. A baseline model will include all the clinical variables. US predictors will be added as covariates to the clinical variables, assuming an additive model. The derived β coefficients were used to calculate prognostic indices, thereby creating weighted prediction models.

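### The clinical reference model omits baseline enthesitis and the tender dactylitis count, so part of any gain credited to ultrasound could come from bedside examination; the likely effect is modest

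*Combined protocol and SAP*

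**What the plan says.** Study objectives, Primary objective, sets the question: "to evaluate the additional value of US-score (US-score PsA-SIR) over clinical examination in detecting patients achieving MDA at 6 months". Under Primary endpoint analysis, "A baseline model will include all the clinical variables", and the US predictors are then added to it. The only list of clinical variables is in the SAP under Clinical predictors, introduced by "Based on the relevant literature clinical variables to be considered in the model include". It has 13 bullets: age, gender, smoking, BMI, PsA subset, time to diagnosis, disease duration, disease activity (DAPSA and BASDAI), HAQ, tender joints or pain, comorbidities, acute phase reactants and treatment. It includes neither an enthesitis measure nor a dactylitis count.

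Both are recorded. The Baseline visit lists an entheseal assessment and the "Tender Dactylitis Count". Methods of assessment defines the first as the LEI plus further sites: "The 4 additional enthesal sites include: quadriceps insertion patella, inferior pole patella, tibial tubercle, insertion plantar fascia". Under Clinical efficacy, an LEI count of at most 1 is one of seven MDA items, of which five must be met. Ultrasonographic assessment covers 44 joints, 36 tendons, 12 entheses and 2 bursae, and the inflammatory subscore counts three entheseal lesions.

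**The concern.** An added-value analysis is only as fair as its comparator. US enters with information on entheses and tendon sheaths, while the clinical model lacks the examiner's own findings on enthesitis and dactylitis. If those findings carry prognostic information that the listed variables do not, US can act as a stand-in for them. The gain would then partly reflect an examination already performed and recorded, rather than something only imaging can show. What is at stake is how the primary result is read: as US over the clinical examination, or as US over a selected part of it.

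**Working it through.** **Is the information carried by another listed item?** DAPSA consists of two joint counts, pain, patient global and CRP. BASDAI is patient-reported. PsA subset 1 is "Monoarticular or asymmetric oligoarthritis with or without dactylitis", so it does not separate patients by dactylitis. The cover is not zero: the protocol describes dactylitis as "swelling of an entire finger due to synovitis, tenosynovitis, enthesitis, and soft tissue edema", so synovitis in an affected digit can enter the joint counts. There is no comparable route for LEI.

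**The plan's own predictor budget (Sample size).** 250 × 0.4 = 100 MDA events. At 10 events per predictor (an assumption; the plan says only that it is a rule of thumb), this gives 10 predictors, as stated. The list costs about 19-23 parameters: age 1, gender 1, smoking 1-2, BMI 1, subset 4, time to diagnosis 1, duration 1, DAPSA 1, BASDAI 1, HAQ 1, tender joints/pain 1-2, fibromyalgia 1, metabolic syndrome 1, acute phase 1-2, treatment 2-3. Two more make 21-25. With 300 less 20% = 240 patients and 240 × 0.4 = 96 events, that is 96/21 = 4.6 to 96/25 = 3.8 events per parameter before any US term.

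**Size of the distortion. All effect inputs are assumed.** Predictors are standardised normal, n = 240, MDA 40%, 2000 simulated trials per cell. logit P(MDA) = a + ln(OR_LEI)·LEI + Σ ln(OR_j)·C_j, with no US effect. The grid is: correlation of each clinical covariate with LEI and with US, r = 0.4 or 0.5; US-LEI correlation 0.3, 0.4 or 0.5; LEI OR 0.5, 0.6, 0.7 or 0.85 per SD; and either one covariate (OR 0.5) or three (OR 0.7 each, mutual correlation 0.5).

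The driver is the US-LEI correlation left after the covariates:

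- One covariate: (ρ − r²)/(1 − r²). This runs from (0.3 − 0.25)/0.75 = 0.07 to (0.5 − 0.16)/0.84 = 0.40.
- Three covariates: (ρ − 1.5r²)/(1 − 1.5r²). This runs from (0.3 − 0.375)/0.625 = −0.12 to (0.5 − 0.24)/0.76 = 0.34.

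Excess = the US gain with LEI absent from both models, minus the US gain with LEI in both.

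| Setting | One covariate | Three covariates |
|---|---|---|
| Excess AUC, whole grid | 0.0001-0.0085 | 0.0001-0.0040 |
| Excess AUC, mid-grid (LEI OR 0.7, US-LEI 0.4) | 0.0009-0.0017 | 0.0001-0.0006 |
| Excess AUC, LEI OR 0.85 | at most 0.0008 | at most 0.0008 |
| Excess IDI, whole grid | 0.0000-0.0105 | 0.0000-0.0059 |

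NRI was not computed, and no run gives the dactylitis count its own term.

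**Outside that grid.** A second simulation used n = 250, one clinical index (OR 0.5) correlated only 0.3 with both US and a single omitted index. At omitted-index OR 0.65 and correlation 0.5 with US, the excess is 0.0084 − 0.0027 = 0.0057. At OR 0.5 it is 0.0145 − 0.0025 = 0.0120, rising to 0.0273 − 0.0022 = 0.0251 if the correlation with US is 0.7. At OR 1.0 it is nil (0.0036 − 0.0035 = 0.0001 at correlation 0.3).

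**Yardstick.** The design improvement, false positives from 0.4 to 0.2 at 0.7 true positives, corresponds to AUC 0.709 to 0.833 under an equal-variance binormal assumption, a gain of 0.124. An excess of 0.009 is 0.009/0.124 = 7% of that.

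**Separate point: change outcomes.** Secondary endpoint analyses apply the same approach to US-damage, mSvH and HRQoL (PsAID) change. All three are measured at baseline, yet the clinical list contains none of these baseline values (HAQ is listed). Baseline US damage appears only among the US predictors. Change from baseline is related to the baseline value through regression to the mean, so that relation can be credited to US. Only the direction is claimed, because the documents give no progression threshold and no score reliability.

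**The case against.** The list is literature-based, and the Background cites obesity, sex, age, disease duration, diagnostic delay and HAQ as predictors, not enthesitis or dactylitis. A patient can fail the LEI item and still reach MDA, and dactylitis is not an MDA item. The list already exceeds 10 predictors. BSA, another MDA item, is missing too. The introductory wording may also be open-ended. On the plan's own measures the effect looks small.

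Most of this stands, and it limits the severity. It does not remove the point. If the list is open-ended, the comparator for the primary analysis is not fixed, and naming these findings still helps. BSA has no counterpart in the US score, whereas enthesitis does. The Background itself names dactylitis and enthesitis among the features that make any single composite index, DAPSA included, an unresolved choice. No reason for the omission is given and no sensitivity model is planned.

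A reader might infer three stronger claims that the documents do not support:

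- **A high false-positive rate for US.** With LEI omitted, a 5% likelihood-ratio test favoured a null US score in 4-40% of simulated trials across the grid. The plan names no such test; it judges added value by AUC, NRI and IDI. The upper end also needs LEI OR 0.5 with US-LEI correlation 0.5. At LEI OR 0.85 the rate is 4-8%.
- **That 44% of the inflammatory score is uncovered examination.** 470 − 44 × (3 + 3) = 206 points do lie outside joint synovitis, but these pool tendons, peritendon tissue and bursae with entheses. Entheseal inflammation is three lesions at 12 sites: 36 of 470 (8%) if scored 0/1, or 60 (13%) with Doppler graded 0-3. The 12 US entheses are not named, so overlap with the LEI sites cannot be verified.
- **That nothing on the list reflects dactylitis.** The joint counts can do so in part.

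**Conclusion.** The omission is confirmed from the text and bears on the primary question. Its consequence is conditional: inflation arises only if the omitted findings predict MDA and remain correlated with US given the listed variables. The documents supply neither quantity, so they neither establish nor exclude it.

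Under the main assumptions, for LEI only, the excess AUC gain is about 0.000-0.009, and 0.002 or less at mid-grid. Larger values, up to 0.025, need a clinical model that is only weakly related to US together with a very strong omitted predictor. That fits poorly with a reference model of 19-23 parameters. This is a modest interpretability issue, worth fixing because it is cheap. It is not evidence that the primary analysis is invalid or that a US gain would be spurious. The missing baseline values for change outcomes are a separate point and do not strengthen this one.

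**What to change.** Prespecify a sensitivity analysis for the primary endpoint. Add one baseline enthesitis measure (LEI, or a single count of LEI plus the additional sites, with the choice named in advance) and the tender dactylitis count to both the clinical and the clinical-plus-US model. Report the US increment in AUC, NRI and IDI beside the main result.

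The cost is SAP wording and one more analysis with about two extra parameters; no new data are needed. Because the expanded models are thin on events, the AUC should be optimism-corrected. Placing both findings in the main model is optional. That would call for penalised estimation or a shorter prespecified list, and which other variables to keep is the sponsor's decision.

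Separately, for the US-damage, mSvH and PsAID change outcomes, put the baseline value of that outcome in both models. For US damage, the US term under test then has to be the inflammatory subscore, since the overall score is the sum of the two subscores (470 + 162 = 632). Because baseline damage is measured with error, this reduces, but does not fully remove, regression to the mean being credited to US.

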Model performance will be evaluated by C-indices (area under the ROC curve, AUC), net reclassification indices (NRI), integrated discrimination improvement (IDI), and plotted ROC curves. NRI can be used to compare the clinical impact of different models (it is a comparison of the proportion of subjects with disease who have appropriately increased risk scores with the new model, and the proportion of subjects without disease who have appropriately decreased risk scores with the new model). IDI represents desired improvements in average sensitivity corrected for undesirable increases in 1-specificity, it therefore compared whether the new models improved sensitivity without affecting specificity.⁽³⁰⁾

Data management and analysis will be performed using RedCap, R, Stata.

SECONDARY ENDPOINT ANALYSES

- to evaluate the additional value of US over clinical examination in detecting patients:
 - achieving MDA at 12 months
 - achieving sustained DAPSA remission at 6 and 12-months
 - achieving DAPSA remission at 6 and 12 months
 - achieving ACR Remission remission at 6 and 12 months
 - with X-ray structural progression (mSVH score) at 12 and 24 months
 - with US structural progression (US-damage score) at 12 and 24 months
 - with functional worsening (Δ HAQ>0.23) at 12 and 24 months
 - with impairment of HRQoL at 12 and 24 months

The same approach followed for the primary endpoint will be followed to evaluate

EXPLORATORY ANALYSES

- to evaluate the relationship between time-integrated US-detected inflammation and US-detected erosions at 12 and 24 months
- to evaluate the comparative effectiveness of different treatment strategies on MDA, DAPSA remission, Δ HAQ>0.23, X-ray progression (mSvHS), US-inflammation score, US-damage score.
- to evaluate the comparative effectiveness of different treatment strategies on MDA, DAPSA remission, Δ HAQ>0.23, , X-ray progression (mSvHS), US-inflammation score, US-damage score.

SAMPLE SIZE

The sample size calculation was done with the objective of minimizing the number of false positives (i.e the number of false non-responsive to treatment) in order to minimize the risk of over-treating patients who actually have a good response to therapy. Therefore, sample size was calculated to minimize this risk by 40% (null hypothesis H0) to 20% (alternative hypothesis H1), maintaining stable at 70% (both for the H0 for both the H1), the percentage of true positives (true unresponsive to therapy).

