The simulations were carried out using the procedure `rocsz` Stata (by M. Pepe)³⁰, which allows to determine the power to detect an improvement in the ROC curve. The procedure requires the specification of the percentage of false positive and true positive both for the null hypothesis is for the alternative hypothesis and the percentage of positive / diseased.

Using the command `rocsz 0.7 0.2, na (150) ndb (100) tnull (0.7) fnull (0.4)` of Stata, 250 patients are sufficient to evaluate the performance of a model (and its ROC curve) with 90% power and 5% alpha. Specifically, we have assumed a 70% and a 20% of subjects true positives and false positives, respectively, according to the alternative hypothesis, a 70% and a 40% of subjects true positives and false positives, respectively, according to the null hypothesis, and a percentage of diseased of 60% (150 of 250 subjects).

Under the assumption of maximum attrition of 20%, the sample size will be increased to 300 patients. The same sample size is sufficient to precisely estimate a logistic model of achievement of a MDA (probability of 0.4 at 6 months) with 10 predictors (rule of thumbs).⁽³¹⁾

Based on the pre-study activities, 35-40 centres will be involved, 15 tertiary and 20-25 secondary rheumatology centres. Assuming 4 eligible patients/months for tertiary and 1/month in secondary centres, a 40% of enrolment rate, about 30 patients/months are expected.

ETHICS

This study will be conducted in accordance with all applicable laws and regulations including, but not limited to, the International Conference on Harmonisation (ICH) Guideline for Good Clinical Practice (GCP), EU guidelines and the ethical principles that have their origins in the Declaration of Helsinki. The institutional review board (IRB)/independent ethics committee (IEC) must review and approve the protocol and informed consent form before any subjects are enrolled. Before any protocol-required procedures are performed, the subject must sign and date the IRB/IEC-approved informed consent form.

Clinical data (including AEs and concomitant medications) will be entered into a validated data capture system provided by the Italian Society for Rheumatology. The data system will include password protection and internal quality checks, such as automatic range checks, to identify data that appear inconsistent, incomplete, or inaccurate.

PUBLICATION RULES

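### The 10-predictor precision statement does not cover a primary model of at least 14 terms, and no optimism correction or calibration check is planned

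*Combined protocol and SAP*

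**What the plan says.** The Statistical Analysis Plan introduces its Clinical predictors list with "Based on the relevant literature clinical variables to be considered in the model include". The list has 13 bullets: four demographic or environmental, seven clinical, one serological and one for therapy. Under Primary endpoint analysis the plan then states: "A baseline model will include all the clinical variables. US predictors will be added as covariates to the clinical variables, assuming an additive model". No selection rule follows.

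The fitted "coefficients were used to calculate prognostic indices, thereby creating weighted prediction models". Performance is described as follows (the quote stops just before the last item, the ROC plots): "Model performance will be evaluated by C-indices (area under the ROC curve, AUC), net reclassification indices (NRI), integrated discrimination improvement (IDI". The secondary endpoints follow the same approach.

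Under Sample size, the number of patients rests on a ROC calculation: "250 patients are sufficient to evaluate the performance of a model (and its ROC curve) with 90% power and 5% alpha". Attrition is then added: "Under the assumption of maximum attrition of 20%, the sample size will be increased to 300 patients". Finally, the same sample "is sufficient to precisely estimate a logistic model of achievement of a MDA (probability of 0.4 at 6 months) with 10 predictors", for which the plan offers only a rule of thumb and a reference.

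No section mentions resampling, a split sample, shrinkage, external validation or a calibration check for the prediction model.

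**The concern.** The precision statement and the primary model do not describe the same analysis. A reader of the Sample size section would think the logistic model had been checked against the available events, but the model that was checked is smaller than the one to be fitted.

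The second gap matters more. The primary question is how much US adds to clinical prediction, and every planned measure of that is calculated in the patients who supplied the coefficients. Apparent performance is then too favourable, and the prognostic index will give predictions that are too extreme in new patients. Nothing in the plan would show by how much.

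**Working it through.** **The plan's own figure.** Inputs from Sample size: 250 patients, MDA probability 0.4, 10 predictors. The rule itself is not stated. Ten events per predictor is an inference, but it reproduces the figure exactly: 250 × 0.4 = 100 events, and 100 / 10 = 10 predictors.

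**Terms in the planned model.** 4 + 7 + 1 + 1 = 13 clinical bullets, plus one US score = 14. This is a floor. One bullet names DAPSA and BASDAI, another names two comorbidities, treatment has three classes and PsA subset has five categories (Clinical assessment). Coding these as 2, 2, 2 and 4 terms, with one for each of the other nine bullets, gives 19 clinical terms, or 20 with US. The documents do not fix the coding.

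**Events per term.** Events = N × 0.4; limit = events / 10.

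| Patients analysed | Events | Limit at 10 per term | Events per term, 14 terms | Events per term, 20 terms |
|---|---|---|---|---|
| 240 (300 less 20%) | 96 | 9.6 | 6.9 | 4.8 |
| 250 | 100 | 10 | 7.1 | 5.0 |
| 300 (no attrition) | 120 | 12 | 8.6 | 6.0 |

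Fourteen terms exceed the limit on every reading of N. So does the 13-term clinical model alone.

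**Optimism, by simulation.** Assumptions: 240 patients, 40% MDA, five active independent predictors, one US term, unpenalised fit. The ranges run over US effects from null to strong, and include a weaker clinical model (AUC 0.65) in the null case.

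| Clinical parameters, plus US | Apparent minus new-patient AUC | Calibration slope in new patients |
|---|---|---|
| 9 | 0.03 to 0.07 | 0.60 to 0.84 |
| 13 | 0.04 to 0.10 | 0.47 to 0.78 |
| 20 | 0.07 to 0.13 | 0.38 to 0.68 |

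**A useless US term.** The apparent AUC gain averages about 0.003, against about -0.002 in new patients. Apparent IDI is about 0.004 against 0.000. Continuous NRI is 0.09 to 0.10 against about 0.01 (the plan does not say which NRI it means). The plan also says "Two-sided p-values will be presented throughout". The likelihood-ratio test for US at the 5% level rejects in about 5 to 6.5% of null simulations.

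**A strong US term.** Read as equal-variance binormal curves, the planned 70%/40% and 70%/20% operating points give AUCs of 0.709 and 0.833. Taking these as clinical alone and clinical plus US (an assumption), the population gain is 0.833 - 0.709 = 0.124.

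| Clinical parameters | Apparent gain | Minus population gain (0.124) | New-patient gain of fitted models | Apparent minus new-patient |
|---|---|---|---|---|
| 9 | 0.115 | -0.009 | 0.132 | -0.017 |
| 13 | 0.110 | -0.014 | 0.135 | -0.025 |
| 20 | 0.103 | -0.021 | 0.138 | -0.035 |

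The new-patient gain rises with model size because the overfitted clinical comparator does worse in new patients.

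**The case against.** The list is introduced as variables for consideration, so it might be a pool of candidates. That reading does not survive the primary-analysis sentence, which puts the whole list in the baseline model. Data-driven selection from 13 candidates would not remove the overfitting in any case.

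The sentence on 10 predictors directly follows the increase to 300 patients. On that reading, 10 predictors have 12 events each and 14 terms have 8.6. This stands: the shortfall at the 14-term minimum is moderate, and the threshold of ten is inferred.

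A model that kept to 10 predictors would overfit as well, with optimism of up to about 0.07 and a slope as low as about 0.60. This also stands. The excess over 10 makes matters worse, but the missing correction is the main fault.

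The strong-US case assumes a US score independent of the clinical variables, which include DAPSA and acute phase reactants. It is only an illustration, and the size of the understatement depends on whether the target is the population gain or the fitted models' gain in new patients.

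The question of which US score enters is largely answered, since the primary objective names the US-score PsA-SIR. What remains is a gap in cross-reference.

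Finally, keeping all the clinical terms leaves the events-per-term deficit in place. That is deliberate, because a thinner comparator can flatter US. In a simulation with a small US effect, the new-patient gain was 0.017 with 20 clinical terms, but 0.040 with 8 terms that left out two of the five active ones.

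**Conclusion.** The point holds. The 10-predictor statement does not cover the primary model, which has at least 14 terms and 6.9 to 8.6 events per term. More important, all performance measures and the prognostic index are apparent values, with no optimism correction or calibration check. The counts come from the documents. The optimism figures rest on the simulation assumptions above, so only their direction and rough size should be relied on.

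Three stronger conclusions are tempting, and the documents do not support them:

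- **The study is too small, or needs 14 × 10 / 0.4 = 350 analysed patients.** The 250 comes from the ROC calculation, which this point does not dispute, and events per term is only a heuristic.
- **Overfitting will make US look better than it is.** The apparent AUC gain is close to unbiased when US adds nothing and is understated when US adds much. IDI and continuous NRI do average above zero for a useless term, but that comes from the lack of correction and barely changes with model size.
- **The false-positive rate is materially raised.** The test for US is at most slightly above its nominal level.

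**What to change.** 1. Under Sample size, keep the ROC justification. Replace the 10-predictor statement with the actual parameter count and the events per parameter at 240, 250 and 300 patients.
2. Under Primary endpoint analysis, report AUC, AUC gain, IDI, NRI (naming the version) and calibration both as fitted and after bootstrap optimism correction. Refit the models with and without US in every resample. State which target the corrected AUC gain is meant to estimate. Apply the same to the secondary endpoints.
3. For clarity, name the overall US-score PsA-SIR as the primary US term and say how the two subscores are used. By the stated ranges the overall score is their sum (470 + 162 = 632), so all three cannot enter together. Fix the clinical list and its coding. Say how tender joints/pain and acute phase reactants are handled, since DAPSA already contains tender joint count, pain and C-reactive protein.

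The cost is SAP wording and modest programming in software the plan already names, with no extra patients or data. Reported performance will look less favourable, and the correction is incomplete. In simulation the bootstrap removed about 80 to 90% of the AUC optimism: for example, with 13 clinical parameters and a strong US effect, 0.854 was corrected to 0.815, against 0.811 in new patients. With 20 clinical parameters and a useless US term, continuous NRI fell from 0.099 to 0.032, against 0.011 in new patients. For a strong US effect, the corrected AUC gain was 0.126 to 0.128, between the population gain of 0.124 and the new-patient gain of 0.134 to 0.138.
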